9.7 Data analysis

Novo Nordisk will be responsible for all statistical analyses.

9.7.1 Evaluability of patients for analysis

There will only be a Full Analysis Set in the study, comprising all patients who have entered into the study fulfilling the inclusion and exclusion criteria and having received at least one administration of rFXIII containing product in the study period. The Full Analysis Set will be identical to the Safety Analysis Set.

 Study ID: NN1841-3868
 CONFIDENTIAL
 Version: 2.0

 UTN: U1111-1131-1558
 Status: Final

 EU PAS No.: ENCEPP/SDPP/3687
 Page: 45 of 65

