9.2.2 Inclusion criteria

- 1. Informed consent obtained before any study-related activities. (Study-related activities are any procedure related to recording of data according to the protocol).
- 2. Able and willing to provide signed informed consent (or patient's legally acceptable representative (LAR) consent, if applicable), as required by local ethics committee, governmental or regulatory authorities.
- 3. Congenital FXIII A-subunit deficiency.
- 4. Actual or planned exposure to the rFXIII.

 Study ID: NN1841-3868
 CONFIDENTIAL
 Version:
 2.0

 UTN: U1111-1131-1558
 Status:
 Final

 EU PAS No.: ENCEPP/SDPP/3687
 Page:
 25 of 65

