9.7.2 Statistical methods

This is a purely descriptive study and the statistical analyses and presentations do not include any testing of pre-specified hypotheses. All analyses and presentations will be based on the Full Analysis Set.

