Use of rFXIII in patients with congenital FXIII A subunit deficiency, other than for prophylactic treatment will listed with patient ID, site, age and alternative purpose of the administration of rFXIII. A subsection for product doses should be added.

Annualised Bleeding rate

This secondary endpoint comprises the annualised rate of bleeding (covering both treatment requiring and non-treatment requiring), occurring from first study related activity after signing the informed consent to the end of patient's participation in the study.

Annualised bleeding rate will be summarised by cause (spontaneous, traumatic and surgery), therapeutic regimen (prophylactic therapy, on-demand therapy, surgery) severity, site of bleeding, haemostatic treatment administered (product name) and haemostatic response. The ratio between traumatic and spontaneous bleeding rates will further be summarised and listed and graphical displays of the bleeding rates and the referred ratio will be presented by patient, ordering the patients according to increasing values.

Protocol	Date:	02 February 2016	Novo Nordisk
Ct., dr. ID. NN11041 2060	Varaion:	2.0	

 Study ID: NN1841-3868
 CONFIDENTIAL
 Version:
 2.0

 UTN: U1111-1131-1558
 Status:
 Final

 EU PAS No.: ENCEPP/SDPP/3687
 Page:
 47 of 65

Bleeding episodes will further be listed, including information about cause, severity, location, date and time of onset, date and time of arrest, product name, dose, haemostatic response, related concomitant illness and related concomitant medication.

Presentation by previously untreated patients

To the extent that the study enrols patients, who receive their first administration of rFXIII within the scope of the present study, a separate presentation of both primary and secondary endpoints will be conducted for this group of patients.

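### The single dosed analysis set drops on-demand patients who never needed rFXIII in the study, so an on-demand bleeding rate by patient regimen would be biased upward by an amount the protocol cannot fix

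*Protocol*

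**What the plan says.** Four statements in the Protocol combine.

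- **Analysis set (9.7.1).** "There will only be a Full Analysis Set in the study". Its members are enrolled, meet the selection criteria, and are limited to those "having received at least one administration of rFXIII containing product in the study period". It is stated to be identical to the Safety Analysis Set.
- **Use of the set (9.7.2).** "All analyses and presentations will be based on the Full Analysis Set". No enrolled set or other denominator is defined.
- **Enrolment (9.2.2).** "Actual or planned exposure to the rFXIII" is enough, so a patient can be enrolled and followed before, or without, any dose in the study. Under 9.2.4, interrupting or stopping rFXIII is not a reason for withdrawal.
- **Bleeding rate (9.7.2.2).** The endpoint counts bleeds whether or not they needed treatment, and its window takes in those "occurring from first study related activity after signing the informed consent to the end of patient's participation in the study". It is summarised by, among other things, "therapeutic regimen (prophylactic therapy, on-demand therapy, surgery) severity, site of bleeding".

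Section 9.1.4 describes once-monthly injection for prophylaxis. Section 9.3 gives treatment of a bleed or surgery as examples of use outside prophylaxis.

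**The concern.** A patient on monthly prophylaxis enters the set whether or not a bleed occurs. A patient treated only on demand enters mainly because something happened that called for rFXIII, and the usual trigger is a bleed. For that group, membership of the set depends partly on the outcome being summarised. Patients who went through follow-up without a treated bleed are left out together with their bleed-free years, and those who bled are kept.

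Requiring a dose is right for adverse drug reactions, since an undosed patient cannot have one. It does not suit a bleeding rate that starts at consent and has an on-demand category. At stake is one descriptive breakdown of a secondary endpoint. The on-demand figure would describe on-demand patients who needed rFXIII, while being labelled as the rate for on-demand therapy.

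**Working it through.** **Inputs from the Protocol.** The entry condition, single set, enrolment rule and time window are as set out above. Study duration is 6 years (9.1.1) and recruitment lasts 4 years at a roughly constant rate (9.5). No on-demand bleeding rate and no number of on-demand patients is given, so the rate below is an assumption shown over a range.

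**Step 1: follow-up.** Section 9.5 states an average participation of about 4.5 years. Constant accrual over 4 years in a 6-year study gives (6 + 2)/2 = 4.0 years. The milestone dates (17 May 2013, 17 May 2017, 29 June 2019) give (6.12 + 2.12)/2 = 4.12. The stated 4.5 would follow from 3 years of accrual, (6 + 3)/2. I use 4.0 and show 4.5 beside it; the conclusion is the same with either.

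**Step 2: formula.** Let rFXIII-treated bleeds be Poisson with rate r per year over T years, with no surgery and no prophylactic dose. The chance of never being dosed is exp(-rT). Excluded patients contribute no treated bleeds, so the mean rate among those kept is r / (1 - exp(-rT)), and the inflation factor is 1 / (1 - exp(-rT)).

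**Step 3: results.** Example: r = 0.3 and T = 4 give exp(-1.2) = 0.301 and 0.3 / 0.699 = 0.429, which is x1.43.

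| Assumed r per year | Excluded, T = 4 | Rate shown, T = 4 | Inflation, T = 4 | Inflation, T = 4.5 |
|---|---|---|---|---|
| 0.1 | 67% | 0.30 | x3.03 | x2.76 |
| 0.25 | 37% | 0.40 | x1.58 | x1.48 |
| 0.3 | 30% | 0.43 | x1.43 | x1.35 |
| 0.5 | 14% | 0.58 | x1.16 | x1.12 |
| 1.0 | 2% | 1.02 | x1.02 | x1.01 |

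Spreading follow-up evenly over 2 to 6 years gives x3.08, x1.62, x1.19 and x1.03 at 0.1, 0.25, 0.5 and 1 per year.

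**Step 4: what moves the size** (follow-up spread over 2 to 6 years).

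- *Surgery as a second way in.* With rFXIII-covered surgery at rate s, unrelated to bleeding, the excluded share at follow-up T becomes exp(-(r + s)T). At r = 0.25, s = 0.3 cuts the inflation from x1.62 to x1.16. A prophylactic dose after a change of regimen works in the same direction.
- *Bleeds not treated with rFXIII.* The endpoint counts these too. If patients are alike, exclusion does not select on them. With 0.5 treated and 0.5 untreated per year, the rate shown is 0.595 + 0.5 = 1.095 against a true 1.0, about x1.1.
- *Differences between patients.* If rates vary (gamma, shape 1) and half of bleeds are treated with rFXIII, those excluded are mostly the low bleeders. Simulated inflation of the total rate is x2.64, x1.77, x1.43 and x1.24 at true total rates of 0.2, 0.5, 1 and 2 per year.

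No scenario gave a factor below 1.

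**The case against.** The case on the other side is substantial.

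- *Not the stated effectiveness measure.* Sections 4.2, 4.6 and 7.1 use the bleeding rate to judge prophylactic treatment, and prophylaxis patients enter the set regardless of bleeding. This stands.
- *No planned comparison.* A reader might infer that an inflated on-demand rate beside the prophylaxis rate makes prophylaxis look better than it is. The documents do not support presenting this as a result of the study: it is single-arm and purely descriptive (9.1.1, 9.7.2), and no section contrasts the two regimens.
- *The breakdown may describe bleeds, not patients.* Regimen is listed with cause, severity and site, and surgery is not a patient group. Section 9.3.4.1 uses similar labels for the circumstances of a bleed. The point therefore holds only if the rate is formed by patient regimen, which is plausible but not stated.
- *The group may be small and the bias slight.* Section 9.5 justifies the size by experience with prophylactic treatment. Section 7.2 says most homozygous patients without prophylaxis bleed recurrently, so the x3 figure at 0.1 per year may be remote. As an illustration only, 3 on-demand patients at 0.3 per year over 4 years would lose about one (3 x 0.30 = 0.9). This limits the size, but the loss of one bleed-free patient still matters in so small a group.
- *An exposed population is defensible for effectiveness of rFXIII.* This also stands. It argues against moving the whole bleeding rate to all enrolled patients, which would bring in people who planned prophylaxis and never started.

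Leaving the matter to the statistical analysis plan is not an answer, because 9.7.1 and 9.7.2 fix one set for every analysis.

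**Conclusion.** The selection is real, and nothing else in the Protocol offsets it. If the regimen breakdown is by patient, the on-demand bleeding rate is biased upward. The size cannot be fixed from the document. With Poisson treated bleeds, each treated with rFXIII, 4 years of follow-up and no surgery, inflation is about x1.4 at 0.3 per year, x1.16 at 0.5 and x1.02 at 1. Entry through surgery or a prophylactic dose makes it smaller; differences between patients make it larger. Confidence is high on direction and low on size.

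The primary safety endpoint, the other safety summaries and the bleeding rate on prophylaxis are untouched. It would go too far to read this as a fault in the Full Analysis Set as such, or as bias in the study's stated measure of effectiveness. It is a cheap improvement to one descriptive breakdown.

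**What to change.** Keep the Full Analysis Set for all safety summaries and for the main bleeding-rate summary. In 9.7.1 and 9.7.2.2, add that the on-demand bleeding rate is also presented for all enrolled eligible on-demand patients, counted from consent, whether or not rFXIII was given in the study. Show how many of them were never dosed, their follow-up time and their bleeds. In the same sentence, say that regimen here means the patient's regimen, so that the denominator is clear.

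The cost is a sentence or two and one extra summary, using data the study already collects. The downside is a second set that differs from the safety set and includes some patients not exposed to rFXIII in the study; the table should be labelled accordingly.

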9.3.2.4 Medical history/concomitant illness

Details on medical history and concomitant illnesses will be recorded at the Visit 1 during a medical interview and review of relevant medical records.

02 February 2016 | Novo Nordisk Protocol Date: 2.0

Final

Study ID: NN1841-3868 Version: CONFIDENTIAL UTN: U1111-1131-1558 Status: EU PAS No.: ENCEPP/SDPP/3687 Page: 33 of 65

All concomitant illnesses must be recorded at study entry, including any recent chronic infectious diseases (in the last 6 months). During the study period any change in concomitant illnesses will be recorded until end of study visit (see section 9.3.2.7).

9.3.2.5 **Details on diagnosis of FXIII CD**

Diagnosis of FXIII deficiency as evidenced in the patient's medical records

- Date of diagnosis.
- Underlying gene defect, if known (FXIII subunit A, FXIII subunit B, other).
 - Genotyping been performed.
 - Mutation been identified (mutation no.).
 - Type of mutation (substitution (missense, nonsense, splice site), deletion, insertion, duplication, inversion, translocation, other).
 - Description of the sequence variant (DNA level, Protein level).
- Type of disorder (FXIII heterozygous, homozygous, other).
- FXIII activity level at time of diagnosis.
- Current FXIII activity level, if available.
- History of anti-FXIII antibodies.

Nature of any antibodies detected in the past:

- Neutralising.
- Non-neutralising.

If any antibodies detected in the past:

- Most recent antibody value.
- Date of most recent antibody value.
- Date of first finding of antibodies.
- Historical maximum antibody value.

Family history (1st degree relatives, other relatives):

- History of antibodies toward FXIII
- Congenital haemostatic disorder (FXIII deficiency (heterozygous, homozygous) and other).
- Congenital pro-thrombotic disorders (FZ Leiden (G1691A), Prothrombin mutation (G20210A), Protein C deficiency, Protein S deficiency, Anti-thrombin deficiency, other.

9.3.2.6 **Concomitant medication**

Definition of concomitant medication: any medication other than rFXIII that is taken during the study, including reported at Visit 1

Details of all concomitant medication must be recorded at study entry (i.e., at the first visit, Visit 1), including any recent vaccinations (in the last 6 months). Any changes in medication must be recorded at each visit (assessment visits and end of study visit) in the CRF.

Protocol Date: 02 February 2016 Novo Nordisk Study ID: NN1841-3868 Version: 2.0

UTN: U1111-1131-1558

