9.3.3 Assessments for safety

Safety information must be collected during each contact (visit or telephone, excluding Visit 1 and safety visits, where the patient is not seeing the Physician or his staff e.g., visits to the laboratory) with the Physician or study site staff. This may be done by posing a simple question such as "have you experienced any problems since the last contact?" For definitions on safety information collected in this study see section 11.2.

After the first administration of rFXIII following enrolment in the study all adverse drug reactions, serious adverse events and medical events of special interest must be collected and reported according to section 11.3.

 Study ID: NN1841-3868
 CONFIDENTIAL
 Version:
 2.0

 UTN: U1111-1131-1558
 Status:
 Final

 EU PAS No.: ENCEPP/SDPP/3687
 Page:
 35 of 65

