9.7.2.1 Primary endpoint

The primary endpoint comprises specific adverse drug reactions in terms of anti-FXIII antibodies, allergic reactions, embolic and thrombotic events and lack of therapeutic effect occurring from first study related activity after signing the informed consent to the end of patient's participation in the study.

The referred specific adverse drug reactions of the primary endpoint (anti-FXIII antibodies, allergic reaction, embolic and thrombotic events and lack of therapeutic effect) will be summarised, displaying the number of reactions and the number and percent of patients experiencing the reaction relevant within system organ class and Medical Dictionary for Regulatory Activities (MedDRA) preferred term. Assessments of anti-FXIII antibodies will be provided by the central laboratory. The endpoint will be presented for all patients as well as by special populations, comprising children, elderly, pregnant and lactating women, and patients with renal insufficiency.

All the specific adverse drug reactions will further be listed with patient ID, site, age, preferred term, date of first dose, date of onset, date of arrest, severity, if it is serious or not, relationship to study drug, action, and outcome.

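### The only safety analysis set is filtered on eligibility, so a treated patient found ineligible would be missing from every safety table and listing

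*Protocol*

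**What the plan says.** Section 9.7.1 fixes the number of sets: "There will only be a Full Analysis Set in the study". It defines that set as "comprising all patients who have entered into the study fulfilling the inclusion and exclusion criteria and having received at least one administration of rFXIII" during the study, and adds that "The Full Analysis Set will be identical to the Safety Analysis Set". Section 9.7.2 then states: "All analyses and presentations will be based on the Full Analysis Set".

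The primary endpoint is itself a safety endpoint. Section 9.7.2.1 says: "The primary endpoint comprises specific adverse drug reactions in terms of anti-FXIII antibodies, allergic reactions, embolic and thrombotic events and lack of therapeutic effect". It is shown as counts of reactions and as counts and percentages of patients, with a listing. Section 9.7.2.2 gives similar tables and listings for serious adverse events, medical events of special interest and medication errors.

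Event collection has no eligibility condition. Section 9.3.3 says that, from the first rFXIII administration after enrolment, "all adverse drug reactions, serious adverse events and medical events of special interest must be collected and reported", and section 11.3 repeats this.

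On eligibility, the third inclusion criterion in section 9.2.2 is "Congenital FXIII A-subunit deficiency". The only exclusion criterion, in section 9.2.3, concerns incapacity, unwillingness or language. Under the details of diagnosis (section 9.3.2.5), the CRF records "Underlying gene defect, if known (FXIII subunit A, FXIII subunit B, other").

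**The concern.** A safety set is normally defined by exposure, so that reactions are counted in everyone who received the product. Here the safety set carries an eligibility filter, and no second set exists to catch those who fail it. The protocol closes the question: a statistical analysis plan that follows section 9.7.1 cannot put these patients back.

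The filter also sits oddly with the rest of the protocol. Under section 9.2.4, ineligibility is not a reason for withdrawal, so such a patient could be followed for years and then appear in no table. Section 10.2 keeps the data already collected from patients who withdraw consent. The plan would thus keep those patients and drop an exposed patient on an eligibility finding.

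At stake is the completeness of the main result of a post-authorisation safety study with about 30 patients, where one patient can decide whether a reaction type is reported as seen or not seen.

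**Working it through.** **Step 1: what the text implies.** Being in the set requires entry, fulfilment of the criteria and at least one administration (9.7.1). All outputs use the set (9.7.2). A patient who entered and was dosed but did not fulfil the criteria fails the second condition and is in no output. That patient's events are still collected (9.3.3, 11.3). The result is events collected but not presented.

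**Step 2: who could be affected.**
- Inclusion criteria 1 and 2 concern consent. Any sensible safety set keeps a consent requirement.
- Inclusion criterion 4 is actual or planned exposure, which a treated patient meets.
- This leaves inclusion criterion 3 (A-subunit deficiency) and the single exclusion criterion. A gene defect that proves not to be A-subunit is one example. A language or cooperation problem recognised after enrolment is another.

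The reach is narrow, and the protocol gives no number of treated but ineligible patients.

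**Step 3: size, as an illustration.** The protocol has no figure to reproduce: section 9.5 has no formal sample size calculation, and section 9.7.2.1 plans counts and percentages only. The intervals below are added to show scale.

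Inputs: n = 30, the anticipated minimum in section 9.5; and, by assumption, 1 to 3 treated but ineligible patients.

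Formula: for x patients with a reaction among n, the percentage is 100·x/n. The exact (Clopper-Pearson) 95% limits are the 0.025 quantile of Beta(x, n−x+1) and the 0.975 quantile of Beta(x+1, n−x). For x = 0 the lower limit is 0 and the upper limit is 1 − 0.025^(1/n).

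| Situation at n = 30 | All treated | Current set |
|---|---|---|
| One reaction, in the one excluded patient | 1/30 = 3.3% (0.1 to 17.2) | 0/29 = 0% (0 to 11.9) |
| Two patients with reactions, one of them the excluded patient | 2/30 = 6.7% (0.8 to 22.1) | 1/29 = 3.4% (0.1 to 17.8) |
| One reaction, not in the one excluded patient | 1/30 = 3.3% (0.1 to 17.2) | 1/29 = 3.4% (0.1 to 17.8) |
| One reaction, three excluded patients, none with it | 1/30 = 3.3% (0.1 to 17.2) | 1/27 = 3.7% (0.1 to 19.0) |

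For the first row, the current-set upper limit is 1 − 0.025^(1/29) = 0.119.

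At n = 40 (10% of the upper population figure of 400 in section 9.5), the first row becomes 1/40 = 2.5% against 0/39 = 0%.

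The change matters only when an excluded patient carries an event. Then a reaction type can go from observed to not observed. Otherwise the percentage moves by a few tenths of a point.

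**The case against.** The strongest case for the plan has five parts.

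**The endpoint concerns A-subunit deficiency.** Sections 8.1.1 and 8.2.1 say so. A patient with another defect is outside the stated endpoint, so leaving that patient out follows the objective. This stands as a reason to show an eligible-set table. It does not justify having no table at all for other exposed patients, and it does not cover a patient with A-subunit deficiency who fails the exclusion criterion.

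**Eligibility may mean status at entry.** It is checked at Visit 1, where the gene defect is also taken from the records, and no text describes later removal. The wording does allow this reading. But a patient who did not fulfil the criteria at entry, and is found out later, still did not fulfil them, and section 9.7.1 does not say which judgement counts.

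**The events are not lost to safety evaluation.** Expedited reporting (11.3) and the safety committee (11.7.1) still see them. This is correct: they are missing from the study's result only.

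**The study is descriptive.** No test or decision rule changes. This is also correct, and it limits the consequence to what the report shows.

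**Few patients are concerned.** This is likely true, given four inclusion criteria and one exclusion criterion.

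Two stronger readings are tempting and should not be made. A reader might infer that misdiagnosed patients are more likely to be reported with lack of effect, so that the exclusion is tied to the outcome. The protocol contains nothing to support that link. A reader might also derive the number of ineligible patients from the statement in section 7.2 that more than 95% of known inherited cases are A-subunit. That share describes all known inherited cases, not a cohort selected for A-subunit deficiency at Visit 1, so it gives no usable frequency.

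**Conclusion.** The point holds in a limited form. Read together, sections 9.7.1 and 9.7.2 put an eligibility filter on the only safety set of a safety study, while sections 9.3.3 and 11.3 collect events without that filter. The gap follows from the text and needs no assumption about frequency.

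Its numerical effect does rest on assumptions: 30 patients, at least one treated but ineligible patient, and an event in that patient. Under those assumptions a single reaction can go from 1/30 to 0/29. Without an event in the excluded patient the effect is negligible. The documents do not show that exclusions will be frequent or related to outcome. The correction is worth making because it is cheap and removes the question before data are seen.

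**What to change.** In section 9.7.1, define the Safety Analysis Set as all consented patients with at least one rFXIII administration in the study period, regardless of the other eligibility criteria. Remove the statement that it is identical to the Full Analysis Set, and adjust section 9.7.2 to match.

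Use the safety set for the summaries and listings of the specific adverse drug reactions and of secondary endpoints 1 to 3. Flag eligibility deviations in the listings. Show the same tables for the eligible A-subunit set, which matches the endpoint wording in section 8.2.1 and remains the set for annualised bleeding rate. Any legal limit on using data without valid consent is a separate matter and is unaffected, since the new set still requires consent.

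Cost: a few sentences and a second column in the safety tables, carried through the special-population, previously untreated and interim presentations. No new data are needed.
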